7. OUTCOME DETERMINATIONS

7.1 Primary Endpoints

The primary endpoint is the time to CV death or first HF hospitalization.

7.2 Secondary Endpoints

- Time to All-cause mortality
- Recurrent hospitalizations
- Days alive and not-hospitalized for CV reasons
- Time to CV death
- Time to first HF hospitalization
- Health Related QOL
- Resource utilization, cost and cost effectiveness
- Safety

7.3 Exploratory Endpoints

• Global Rank Endpoint, incorporating death, hospitalization, and change in quality of Life

• Win-ratio, incorporating death, hospitalization, and change in quality of life

7.4 Safety

The main safety objectives in GUIDE-IT are to characterize the risk profiles of the two management strategies and to monitor for unanticipated risks to study participants. In this study, all medications and procedures commonly used or performed as a part of standard of care for the management of HF have well defined safety profiles. For this trial, reporting is primarily governed by the Common Rule (45 CFR Part 46, Subpart A), Investigational Device Exemptions (Part 812), as well as ICH Guidelines, IRBs and local regulations.

The investigator is responsible for monitoring the safety of subjects enrolled into the study at the study site. The investigator or qualified designee will enter the required initial and follow-up information regarding events into the appropriate module of the eCRF within InForm. Investigators are to report serious adverse events in accordance with their local IRB requirements. Investigators should follow usual clinical practices at their institution for reporting to regulatory authorities serious, unexpected events related to standard of care medications and devices.

7.4.1 Definitions

An adverse event (AE) is any untoward medical occurrence in a patient or clinical investigational subject administered an investigational intervention and which does not necessarily have a causal relationship with this treatment. An AE can therefore be any unfavorable and unintended sign (including an abnormal laboratory finding), symptom, or disease temporally associated with the investigational intervention, whether or not considered related to the investigational intervention (ICH1996).

A serious adverse event (SAE) is any adverse event that may result in any of the following outcomes:

- Death
- Is life-threatening
- Results in persistent or significant disability/incapacity
- Is a congenital anomaly/birth defect
- Important medical event that may not result in death, be life-threatening, or require hospitalization may be considered a SAE when, based upon appropriate medical judgment, it may jeopardize the patient or subject and may require medical or surgical intervention to prevent one of the outcomes listed above

AEs of Interest for the GUIDE IT trial, which may or may not meet serious criteria, include any of the following:

- Symptomatic hypotension
- Symptomatic bradycardia
- Hyperkalemia (Potassium > 6.0 meq/dl or requiring change in therapy)
- Worsening renal function (increase in creatinine by 0.5 mg/dl from last visit or requiring change in therapy)

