2.5 Design of GUIDE-IT: Rationale for an Unblinded Study

GUIDE-IT will be an unblinded trial because blinding would eliminate one potentially important mechanism of treatment effect: the impact of patient knowledge of their own natriuretic peptide levels on adherence and health-related behaviors. Blinding GUIDE-IT would remove the patient from the critical role of active partnership in the management of his or her disease and would not reflect how biomarker-guided therapy will ultimately be used in practice, thus raising important issues about generalizability. We have taken multiple steps to minimize potential biases related to lack of blinding, including the use of an objective primary endpoint (cardiovascular death or HF hospitalization) and centralized adjudication of events by a Clinical Event Committee blinded to treatment assignment.

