6.3.3 Follow-up Assessments after Adjustment of Therapy or Hospitalization

There will be a 2-week (± 1 week) reassessment for patients who have a change in therapy, resulting from clinical findings or natriuretic peptide levels. **This follow up can be in person or a remote laboratory evaluation at the discretion of the treating physician**. This follow-up assessment will include a brief clinical assessment (if in person visit), measurement of renal function and electrolytes, and local laboratory NT-proBNP measurement (biomarker-guided arm only. Follow-up assessments will continue every 2 weeks until therapeutic targets are reached, or the investigator determines that further titration of therapy is not possible. Patients hospitalized for HF during the study will have a 2-week follow-up study visit post discharge to reassess and adjust medical therapy, which will include all standard follow-up assessments as defined above (Section 6.3.2).

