6.5 Minimizing Potential Bias

To address potential effects of an unblinded trial design on outcome determination, we have chosen an objective primary endpoint (HF hospitalization or CV death) and will use a blinded Clinical Endpoints Committee (CEC) to classify potential endpoints. Source data (i.e., history, laboratory procedures and discharge summaries) on all deaths and hospitalizations will be reviewed by the CEC in a consistent, standardized and unbiased manner. Final cause for each event will be adjudicated using definitions that will be established in the CEC Charter.

Another potential source of bias relates to the possibility that the greater frequency of medical visits due to natriuretic peptide guidance will lead to improved patient outcomes through a mechanism other than

biomarker-guided titration of HF therapy. While GUIDE-IT will mandate frequent visits in the usual-care group (as consistent with standard practice), any observed differential in the number of medical interventions (driven by out-of-range natriuretic peptide levels in apparently stable patients) may be the mechanism by which any treatment effects are realized. The alternative of mandating extra clinical visits for the usual-care arm to mirror the visit pattern of the biomarker-guided arm carries risk of biasing the trial results. Those extra visits, which would not occur in regular clinical practice, could lead to extra testing and treatment modifications that result in the outcomes of the two arms converging, thus masking a real treatment benefit. While there is no perfect solution to this problem, we will have detailed data on the content of each clinic visit in both treatment arms; thus, we will determine how often these visits included significant modifications of medical therapy.

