6.6 Maximizing Protocol Adherence

In order to persuasively test the primary hypothesis of GUIDE-IT, we will maximize adherence to the assigned strategies. In the case of the biomarker-guided arm, the investigators will act on above-target NT-proBNP levels even in the absence of worsening symptoms or signs of HF. Similar to studies of intensive glycemic control or blood pressure control, adherence monitoring and feedback to providers will be critical to the success of GUIDE-IT. To ensure that investigators adhere to the protocol, GUIDE-IT will convene an Adherence Committee to focus on investigator education and training.

Based on our experience in prior studies to identify and correct non-adherence, adherence monitoring and intervention will take a stepped approach. For example, the clinical coordinating center (CCC) will collect patient feedback on adherence. Investigators at sites with two episodes of non-adherence will be contacted to review episodes and the importance of adherence will be reemphasized. Reports on adherence will be provided to the Executive Committee. The Executive Committee will consider suspending enrollment at sites not performing at appropriate levels. Adherence performance will be used in determining authorship of trial manuscripts. Although we recognize that such substantial efforts at ensuring investigator adherence are not practical in all real-world settings, we believe they are critical for a proof-of-concept efficacy trial such as GUIDE-IT.

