7.4.2 Reporting Adverse Events

Adverse Events that do not meet SAE criteria and that are not an AE of Interest will not be reported in the InForm database.

SAEs and AEs of Interest that occur from randomization through completion of the final study visit will be reported in the InForm database in the following manner:

- AEs of Interest that do not meet SAE criteria will be recorded on the AE eCRF.
- SAEs that require hospitalization will be reported on the HOSP eCRF noting the reason for the hospitalization. AEs of Interest that require hospitalization will be reported on the HOSP eCRF rather than the AE eCRF.
- Secondary SAEs that may occur while a subject is hospitalized due to a different reason will be reported on the AE eCRF.
- Deaths will be reported on the DEATH eCRF.
- If the subject was hospitalized for the event that led to death, the event will need to be reported both on the HOSP eCRF and the DEATH eCRF.

The Investigator will follow all SAEs and AEs of Interest until resolution, stabilization or the event is otherwise explained.

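### Hyperkalemia and renal events as reported mix true harm with unequal laboratory detection and unblinded treatment decisions; a threshold-based companion comparison on the common visits is needed

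*Protocol*

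**What the plan says.** **Event definitions (7.4.1).** Two of the four adverse events of interest are laboratory events with two limbs each: "Hyperkalemia (Potassium > 6.0 meq/dl or requiring change in therapy" and "Worsening renal function (increase in creatinine by 0.5 mg/dl from last visit or requiring change in therapy". Below, the numeric criterion is the threshold limb and the treatment criterion is the action limb.

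**Capture (7.4.2).** "SAEs and AEs of Interest that occur from randomization through completion of the final study visit will be reported in the InForm database". Nothing restricts these events to scheduled draws. Adverse events that are neither serious nor of interest are not entered in the database.

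**Blinding and adjudication.** Section 2.5: "GUIDE-IT will be an unblinded trial because blinding would eliminate one potentially important mechanism of treatment effect". Section 5.1 leaves guided-arm treatment decisions to the treating physician. Blinded adjudication (6.5, 9.4, 10.7) covers deaths, hospitalizations and primary outcome events; it is not extended to adverse events of interest.

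**Blood draws.** Creatinine, BUN and electrolytes are scheduled identically in both arms (6.3.2, Appendix A). Section 6.3.3 adds a reassessment with renal function and electrolytes 2 weeks after a change in therapy, in either arm, and then: "Follow-up assessments will continue every 2 weeks until therapeutic targets are reached, or the investigator determines that further titration of therapy is not possible". In the guided arm only, section 6.6 adds that "the investigators will act on above-target NT-proBNP levels even in the absence of worsening symptoms or signs of HF".

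**What the protocol says about the imbalance.** Section 6.5 names "the greater frequency of medical visits due to natriuretic peptide guidance" as a possible source of bias in patient outcomes and explains why visits are not matched. Its answer is to record the content of each visit. Harms are not mentioned.

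**Purpose.** Safety is a secondary endpoint (1.2, 7.2), and section 7.4 states: "The main safety objectives in GUIDE-IT are to characterize the risk profiles of the two management strategies".

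**The concern.** For a fair comparison of harms, the same abnormality should have the same chance of being counted in either arm. Two features work against that.

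- **Detection.** A fixed potassium cut-off is crossed more often when potassium is measured more often. Patients enter with NT-proBNP above 2000 pg/mL or BNP above 400 pg/mL, and the guided target is below 1000 pg/mL. Many guided patients will therefore start above target and can enter the 2-week loop for a reason that does not exist in usual care.
- **Action.** Through the action limb, a value below the cut-off becomes an event if a physician who knows the assignment changes treatment, and does not if the physician watches it.

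These are two of the four harms tracked by name, and most other non-serious events are not collected. If hyperkalemia or renal events differ between arms, a reader will want to know whether the strategy caused more of them or whether more were found and acted on. The events as reported do not answer that.

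**Working it through.** The protocol gives no rate or power for these events, so there is no figure to reproduce. The steps below size the mechanism under stated assumptions.

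**1. Scheduled draws (6.3.2, Appendix A).** Weeks 2 and 6 and months 3, 6, 9 and 12 give 6 draws by month 12. Months 15, 18, 21 and 24 bring the total to 10. With 1,100 patients at 35 per month (8.4), accrual takes 1100/35 = 31.4 months. With at least 12 and at most 24 months of follow-up, and ignoring death and loss, the share of patients reaching months 15, 18, 21 and 24 is 1 − 3/31.4, 1 − 6/31.4, 1 − 9/31.4 and 1 − 12/31.4. These sum to 3.0, so the mean is 6 + 3.0 = about 9 scheduled draws per patient.

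**2. Possible extra draws.** A patient in the 2-week loop throughout the first 3 months has draws at weeks 4, 8 and 10 beyond the schedule, so up to 3. This is a ceiling for that period and is not the between-arm difference, because usual-care patients also enter the loop. I assume a net excess of k = 1, 2 or 3 draws per guided patient.

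**3. Threshold limb with no true difference.** Let q be the chance per draw of exceeding the cut-off, equal in both arms, with draws independent (assumptions). The risk ratio is [1 − (1 − q)^(n+k)] / [1 − (1 − q)^n]. For q from 0.2% to 2%:

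| Scheduled draws n | k = 1 | k = 2 | k = 3 |
|---|---|---|---|
| 9 | 1.10–1.11 | 1.20–1.22 | 1.30–1.33 |
| 6 (12 months) | 1.16–1.17 | 1.31–1.33 | 1.46–1.50 |

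Example: n = 6, k = 2, q = 2% gives 1 − 0.98^6 = 11.4% against 1 − 0.98^8 = 14.9%, ratio 1.31. At 550 per arm, the chance of a nominally significant difference (2-sided 0.05) is then about 41%. With one extra draw it is about 14%.

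**4. Action limb.** Assume potassium is normal with mean 4.4, 4.5 or 4.6 and SD 0.45, 0.5 or 0.5 respectively, on the scale of the 6.0 cut-off, and that action is considered for values from 5.5 to 6.0. The event probability per draw is P(K > 6.0) + a × P(5.5 < K ≤ 6.0), where a is the share of such values acted on. Over 9 draws, with identical potassium in both arms:

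| Share acted on, usual care / guided | Equal draws | 2 extra guided draws |
|---|---|---|
| 30% / 50% | 1.49–1.60 | 1.79–1.95 |
| 50% / 30% | 0.62–0.67 | 0.76–0.81 |

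At 30% action, 80% to 92% of counted events come from the action limb. That limb can dominate the count, and its direction follows entirely from the assumed action rates.

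**5. Threshold limb for creatinine.** The reference is the last visit. More frequent visits give more chances to detect a rise but also a more recent reference: 0.6 mg/dl spread evenly over 13 weeks is 0.6/6.5 = 0.09 mg/dl per 2-week interval and would not count. The bias could run either way.

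**6. Numeric events on scheduled draws only.** Under the distributions in step 4, potassium above 6.0 at any of 9 draws occurs in 0.17% to 2.3% of patients, about 1 to 13 per arm of 550.

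**The case against.** - **Sections 7.4.1 and 7.4.2 are reporting rules.** No section says how adverse events of interest will be compared between arms; the only stated safety test is for SAEs (8.14, 10.11), and a SAP could restrict the draws used. This stands: the protocol does not prescribe a biased test. But it does fix the mixed definition and the capture rule, and both feed any comparison of the events as reported.
- **The loop runs in both arms.** Usual care also has targets, the guideline doses, and the loop ends when further titration is not possible. This stands, so the excess is unknown. The guided arm nevertheless has a trigger that usual care lacks, and section 6.5 itself anticipates more visits there.
- **The action limb need not inflate guided-arm harm.** A reader might infer that physicians told to intensify therapy will record more events. Section 6.6 requires action on NT-proBNP, not on potassium, and adherence pressure could make those physicians slower to change treatment for a borderline value. The protocol does not settle this, and step 4 shows either direction.
- **Extra visits and titration belong to the strategy.** Hyperkalemia that forces a treatment change is a real cost of it. This stands, and is why the all-events comparison should remain.
- **A scheduled-visit comparison loses events.** An excursion found at week 8 and corrected before month 3 disappears from it, probably more often in the arm that titrates more. This stands too: such a comparison can support the all-events one but not replace it.

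**Conclusion.** The concern holds as a problem of interpretation. Compared as reported, hyperkalemia and worsening renal function combine true harm, unequal detection and unblinded action, and the protocol offers no safeguard for harms.

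The size is not given. For threshold potassium events, an assumed excess of 1 to 3 draws yields a null risk ratio of about 1.1 to 1.3 over 9 draws and 1.16 to 1.5 over 6; one extra draw distorts little. These figures assume independent draws with equal risk per draw. The action limb and the creatinine threshold limb could each bias in either direction.

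Two stronger readings are not supported. One is that the definitions inflate guided-arm harm overall: that needs action rates and draw excesses the protocol does not state. The other is that the all-events comparison is invalid: it remains the direct answer on what each strategy entails, though it cannot separate detection from harm.

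**What to change.** Keep the definitions, site reporting, patient monitoring and the all-events comparison of the two strategies. Add, in the protocol or the SAP:

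1. A prespecified companion comparison of hyperkalemia and worsening renal function by arm, on numeric thresholds only, using creatinine and potassium from the visits scheduled identically in both arms (2 and 6 weeks, then every 3 months).
2. An all-events table by arm split by source: threshold or action only, and scheduled visit or 6.3.3 or other draw, with the number of draws per arm.
3. The same split in DSMB tables that show these events.

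The potassium limit is printed per decilitre. The calculations above assume that the number is meant on the usual per-litre scale; the unit should be reconciled before a numeric comparison is programmed.

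**Cost.** A little more analysis work; the scheduled laboratory values are already collected in both arms. The event form should let the limb and the draw behind each event be identified. The companion comparison will have few potassium events and will omit some real events around titration, so it supports the all-events comparison and does not replace it.

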6.3.2 Follow-Up Visits

Follow-up visits will occur at 2 weeks, 6 weeks, 3 months, and then every 3 months for the remainder of the study duration period (minimum of 12 months and a maximum of 24 months). All study visits will be completed within a ± 1-week window. The following assessments will occur at each follow-up study visit.

- Focused interval history and physical examination
- CV medication history
- Document rationale for changes in HF therapy
- Serum creatinine, BUN, and electrolytes (local laboratory)
- NT-proBNP (local laboratory, Biomarker-guided Arm only)
- QOL questionnaire (as described in 6.7)
- Medical resource use and cost assessment
- Ascertainment of interval safety events and endpoints
- Biomarker collection for biorepository (as described in 6.4)

Subjects in the biomarker-guided arm will have NT-proBNP testing performed in the local laboratory by appropriately trained personnel, and these values will be used for the purposes of titrating therapy to the

protocol-specified target. If therapy is adjusted, the changes in therapy and the rationale for the adjustment (e.g. clinical reason, not at biomarker target) will be recorded on the eCRF. Subjects in the usual care arm will not have routine assessment of natriuretic peptides except for compelling medical reasons.

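### The creatinine criterion for worsening renal function is measured from the last visit, so the event count depends on visit frequency, which is expected to differ by arm; the net direction of the error is unknown.

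*Protocol*

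**What the plan says.** Section 7.4.1 of the Protocol lists the renal event of interest as "Worsening renal function (increase in creatinine by 0.5 mg/dl from last visit or requiring change in therapy". It has two limbs: a laboratory limb with a moving reference, and a limb that depends on a treatment decision. No renal criterion refers to baseline.

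The regular schedule in section 6.3.2 is the same in both arms: "Follow-up visits will occur at 2 weeks, 6 weeks, 3 months, and then every 3 months". Section 6.3.3 then adds a 2-week "reassessment for patients who have a change in therapy, resulting from clinical findings or natriuretic peptide levels", which includes "measurement of renal function and electrolytes, and local laboratory NT-proBNP measurement" (the NT-proBNP part in the guided arm only). These assessments repeat: "Follow-up assessments will continue every 2 weeks until therapeutic targets are reached, or the investigator determines that further titration of therapy is not possible". On their form, the section says: "This follow up can be in person or a remote laboratory evaluation at the discretion of the treating physician". The Protocol does not say whether such an assessment is a visit for the purpose of the renal definition.

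Section 6.6 has guided-arm investigators respond to NT-proBNP above target even in patients who are not clinically worse. Sections 5.2 and 6.3.2 exclude routine natriuretic peptide testing in usual care. Section 6.5 discusses "the possibility that the greater frequency of medical visits due to natriuretic peptide guidance will lead to improved patient outcomes" and argues against giving usual care a matching visit pattern.

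**The concern.** A difference from the previous value measures change per interval, not change since randomization. If intervals are shorter in one arm, the same 0.5 mg/dl threshold is a different criterion there. A slow decline is divided into steps too small to count. A brief rise that would fall between two 3-monthly visits is caught, and each extra pair of measurements is another chance for noise to cross the threshold.

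Safety is a secondary endpoint (section 7.2), and its main objective is to characterize the risk profiles of the two strategies (section 7.4). Under section 7.4.2, non-serious events outside the four events of interest are not recorded at all. The guided arm's list of options in section 5.1 includes drugs whose use the Protocol itself ties to renal function. A between-arm comparison of the renal event is therefore one that readers will look for, and as defined it mixes renal effect with measurement frequency.

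**Working it through.** The Protocol gives no expected rate or power for this event, so there is no figure to reproduce.

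**Inputs from the Protocol:** threshold 0.5 mg/dl (7.4.1); scheduled spacing of 3 months after month 3, taken as 12 weeks (6.3.2); extra assessments 2 weeks apart (6.3.3).

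**Assumed, because the Protocol does not give them:** the shape of the renal course, the within-patient SD of creatinine (σ, varied from 0.08 to 0.25 mg/dl) and the number of extra assessments. All results concern the creatinine limb alone.

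**Step 1, no noise.** A linear rise R over 12 weeks, measured every s weeks, gives steps of R × s / 12. For R = 0.6:
- s = 12: 0.6, which counts
- s = 6: 0.3; s = 4: 0.2; s = 2: 0.1; none counts

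The smallest 12-week rise that counts is 0.5 × 12 / s: 0.5 mg/dl at 12-weekly measurement and 3.0 mg/dl at 2-weekly.

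**Step 2, noise, one 12-week interval.** The difference of two measurements has SD σ√2, so one step with true change δ is flagged with probability 1 − Φ((0.5 − δ)/(σ√2)). For δ = 0.6 and σ = 0.15 this is 1 − Φ(−0.1/0.212) = 68%. The six linked 2-weekly steps were simulated (200,000 patients per scenario).

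| σ | Rise 0.6: 12-weekly | Rise 0.6: 2-weekly | No rise: 12-weekly | No rise: 2-weekly |
|---|---|---|---|---|
| 0.08 | 81% | 0.1% | 0% | 0% |
| 0.15 | 68% | 17% | 1% | 5.5% |
| 0.25 | 61% | 61% | 8% | 41% |

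**Step 3, months 3 to 12, onset uniform between months 3 and 9.** Share flagged at any pair of consecutive measurements (at least 40,000 simulated patients per cell):

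| Course | σ | 3-monthly | 2-weekly |
|---|---|---|---|
| Linear 0.8 over 2 months | 0.10 | 83% | 6% |
| Linear 0.6 over 3 months | 0.10 | 40% | 2% |
| Linear 1.0 over 1 month | 0.10 | 98% | 67% |
| Sustained step of 0.7 | 0.10 | 92% | 92% |
| Transient 0.7 for 1 month | 0.10 | 31% | 92% |
| Transient 0.7 for 2 weeks | 0.10 | 15% | 92% |
| Linear 0.6 over 3 months | 0.20 | 57% | 64% |
| Linear 0.6 over 3 months | 0.25 | 64% | 87% |
| No true rise | 0.20 | 11% | 52% |

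Continuous 2-weekly measurement is the extreme. With a single reassessment 2 weeks after each 3-monthly visit, the first row is 83% against 68%.

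**Step 4, a fixed reference.** In the setting of step 2 with a 0.6 rise, take the value at the common scheduled visit minus baseline. 12-weekly against 2-weekly measurement then gives 81% v 81%, 68% v 68% and 61% v 61% for the three SDs. Using baseline as reference but counting at every extra assessment gives 81% v 86%, 68% v 79% and 61% v 79%. Both elements are needed: a fixed reference and common time points.

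**The case against.** A reader might infer that the definition biases the safety comparison in favour of the guided arm by hiding renal harm. The documents do not support that. It follows only for slow, steady rises with small measurement error. Step 3 shows the opposite for transient rises and for larger SDs, and the Protocol gives no basis for choosing among these courses.

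Four further points narrow the claim:
- The limb for events requiring a change in therapy counts a gradual decline whatever the step size, and patients under 2-weekly review are those whose therapy is being adjusted. This stands in part: declines that lead to no treatment change are still missed, and the limb rests on judgement in an unblinded trial and on how often the patient is seen.
- The 2-week reassessments apply in both arms and stop when targets are reached or titration is exhausted. The excess in the guided arm is expected, not scheduled, so the extreme grid overstates the contrast.
- If the last visit means the last regular visit, the problem largely disappears. The text does not say so, and since a reassessment may be a remote laboratory test, sites could read it either way.
- Section 7.4 tells sites what to report and fixes no between-arm test on this count. The statistical analysis plan, not shown here, may use creatinine change from baseline. But the reporting definition is fixed in the Protocol, and any comparison of reported events inherits it.

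**Conclusion.** The point holds without a stated direction. The creatinine limb has a moving reference, and the Protocol itself expects measurement to be more frequent in the guided arm, so an identical renal course can yield different counts by arm. Gradual decline is under-counted under frequent measurement; transient rises and noise are over-counted. The net sign cannot be determined from the document.

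The size depends on the assumed course, SD and number of extra assessments. In the examples it runs from no difference (a sustained step of 0.7), through 83% against 68% (linear 0.8, one extra reassessment per quarter), to 83% against 6% at the extreme, and it reverses to 31% against 92% for a 1-month transient rise. These are illustrations of the mechanism, not predictions for this trial. The primary endpoint is not affected.

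**What to change.** 1. Keep the section 7.4.1 definition for site reporting, and state whether the last visit includes the 2-week reassessments of section 6.3.3, in person or remote.
2. For the between-arm safety comparison, add a creatinine rise of at least 0.5 mg/dl from the randomization value, counted only at visits scheduled for both arms: 2 weeks, 6 weeks, 3 months and every 3 months thereafter.
3. Report rises found only at extra assessments by arm alongside that comparison, not in place of it, so that transient rises during titration stay visible. Show the number of creatinine measurements per arm with it.

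The cost is one sentence of definition and one more table. Creatinine at randomization and at every scheduled visit is already collected in both arms (sections 6.3.1 and 6.3.2, Appendix A). One limitation should be stated: patients found during a heart failure admission are not randomized until discharge (section 6.1), so their randomization value may not be a stable reference. If the statistical analysis plan already contains such a summary, only item 1 and the by-arm listing in item 3 remain.
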